Appendix 3. Measurement Tools

Appendix 3.1 Dialysis Symptom Index

Instructions

Below is a list of physical and emotional symptoms that people on dialysis may have. For each symptom, please indicate if you had the symptom during the past week by circling "yes" or "no." If "yes", please indicate how much that symptom bothered you by circling the appropriate number.

	During the past of Did you experient		If "yes": How much did it bother you?						
	symptom?	Not At All	A Little	Some- what	Quite a Bit	Very Much			
1.	Constipation	NO							
		YES \rightarrow	1	2	3	4	5		
2.	Nausea	NO							
		YES \rightarrow	1	2	3	4	5		
3.	Vomiting	NO							
		YES \rightarrow	1	2	3	4	5		
4.	Diarrhea	NO							
		YES \rightarrow	1	2	3	4	5		
5.	Decreased appetite	NO							
		YES \rightarrow	1	2	3	4	5		
6.	Muscle cramps	NO							
		YES \rightarrow	1	2	3	4	5		
7.	Swelling in legs	NO							
		YES \rightarrow	1	2	3	4	5		
8.	Shortness of breath	NO							
		YES \rightarrow	1	2	3	4	5		
9.	Lightheadedness or	NO							
	dizziness	YES \rightarrow	1	2	3	4	5		
10.	Restless legs or difficulty keeping	NO							
	legs still	YES \rightarrow	1	2	3	4	5		

	During the past we straight to the contract of		If "yes": How much did it bother you?						
	symptom?	e uns	Not At All	A Little Bit	Some- what	Quite a Bit	Very Much		
11.	Numbness or tingling in feet	NO							
12.	Feeling tired or lack	$\begin{array}{c} \text{YES} \rightarrow \\ \text{NO} \end{array}$	1	2	3	4	5		
	of energy	YES \rightarrow	1	2	3	4	5		
13.	Cough	NO				.			
14.	Dry mouth	$\begin{array}{c} \text{YES} \rightarrow \\ \text{NO} \end{array}$	1	2	3	4	5		
		YES \rightarrow	1	2	3	4	5		
15.	Bone or joint pain	NO							
16.	Chest pain	$\begin{array}{c} \text{YES} \rightarrow \\ \text{NO} \end{array}$	1	2	3	4	5		
	-	$YES \rightarrow$	1	2	3	4	5		
17.	Headache	NO							
18.	Muscle soreness	$\begin{array}{c} \text{YES} \rightarrow \\ \text{NO} \end{array}$	1	2	3	4	5		
		$YES \rightarrow$	1	2	3	4	5		
19.	Difficulty concentrating	NO							
20.	Dry skin	$\begin{array}{c} \text{YES} \rightarrow \\ \text{NO} \end{array}$	1	2	3	4	5		
		$YES \rightarrow$	1	2	3	4	5		
21.	Itching	NO							
22.	Worrying	$\begin{array}{c} \text{YES} \rightarrow \\ \text{NO} \end{array}$	1	2	3	4	5		
		$YES \rightarrow$	1	2	3	4	5		

During the past week:					If "yes": How much did it bother you?						
Did you experience this symptom?				Not At All	A Little Bit	Some -what	Quite a Bit	Very Much			
23.	Feeling nervous	NO									
		YES	\rightarrow	1	2	3	4	5			
24.	Trouble falling	NO									
	asleep	YES	\rightarrow	1	2	3	4	5			
25.	Trouble staying asleep	NO									
		YES	\rightarrow	1	2	3	4	5			
26.	Feeling irritable	NO									
		YES	\rightarrow	1	2	3	4	5			
27.	Feeling sad	NO									
		YES	\rightarrow	1	2	3	4	5			
28.	Feeling anxious	NO									
		YES	\rightarrow	1	2	3	4	5			
29.	Decreased interest in sex	NO									
	III SCA	YES	\rightarrow	1	2	3	4	5			
30.	Difficulty becoming sexually aroused	NO									
	somulity aroused	YES	\rightarrow	1	2	3	4	5			

Appendix 3.2 EuroQol 5D-5L Health-Related Quality of Life Questionnaire

Health Questionnaire

English version for Canada

[figure not shown]
Canada (English) © 2009 EuroQol Group EQ-5D™ is a trade mark of the EuroQol Group

MOBILITY I have no problems in walking about I have slight problems in walking about I have moderate problems in walking about I have severe problems in walking about I am unable to walk about SELF-CARE I have no problems washing or dressing myself I have slight problems washing or dressing myself I have moderate problems washing or dressing myself I have severe problems washing or dressing myself I am unable to wash or dress myself **USUAL ACTIVITIES** (e.g. work, study, housework, family or leisure activities) I have no problems doing my usual activities I have slight problems doing my usual activities I have moderate problems doing my usual activities I have severe problems doing my usual activities I am unable to do my usual activities **PAIN / DISCOMFORT** I have no pain or discomfort I have slight pain or discomfort I have moderate pain or discomfort I have severe pain or discomfort I have extreme pain or discomfort **ANXIETY / DEPRESSION** I am not anxious or depressed I am slightly anxious or depressed I am moderately anxious or depressed I am severely anxious or depressed

Under each heading, please tick the ONE box that best describes your health TODAY.

- We would like to know how good or bad your health is TODAY.
- This scale is numbered from 0 to 100.
- 100 means the best health you can imagine.
 0 means the worst health you can imagine.
- Mark an X on the scale to indicate how your health is TODAY.
- Now, please write the number you marked on the scale in the box below.

YOUR HEALTH TODAY =

Appendix 3.3: Godin Leisure-Time Exercise Questionnaire

INSTRUCTIONS

In this excerpt from the Godin Leisure-Time Exercise Questionnaire, the individual is asked to complete a self-explanatory, brief four-item query of usual leisure-time exercise habits.

CALCULATIONS

For the first question, weekly frequencies of strenuous, moderate, and light activities are multiplied by nine, five, and three, respectively. Total weekly leisure activity is calculated in arbitrary units by summing the products of the separate components, as shown in the following formula:

Weekly leisure activity score = $(9 \times \text{Strenuous}) + (5 \times \text{Moderate}) + (3 \times \text{Light})$

The second question is used to calculate the frequency of weekly leisure-time activities pursued "long enough to work up a sweat" (see questionnaire).

EXAMPLE

Strenuous = 3 times/wk

Moderate = 6 times/wk

Light = 14 times/wk

Total leisure activity score = $(9 \times 3) + (5 \times 6) + (3 \times 14) = 27 + 30 + 42 = 99$

Godin Leisure-Time Exercise Questionnaire

1. During a typical **7-Day period** (a week), how many times on the average do you do the following kinds of exercise for **more than 15 minutes** during your free time (write on each line the appropriate number).

a) STRENUOUS EXERCISE (HEART BEATS RAPIDLY)

(e.g., running, jogging, hockey, football, soccer, squash, basketball, cross country skiing, judo, roller skating, vigorous swimming, vigorous long distance bicycling)

b) MODERATE EXERCISE (NOT EXHAUSTING)

(e.g., fast walking, baseball, tennis, easy bicycling, volleyball, badminton, easy swimming, alpine skiing, popular and folk dancing)

c) MILD EXERCISE (MINIMAL EFFORT)

(e.g., yoga, archery, fishing from river bank, bowling, horseshoes, golf, snow-mobiling, easy walking)

Times Per Week

2. During a typical **7-Day period** (a week), in your leisure time, how often do you engage in any regular activity **long enough to work up a sweat** (heart beats rapidly)?

OFTEN	SOMETIMES	NEVER/RARELY
1. 🖓	2. 🖓	3. 🖓

The Shuttle Walking Test (SWT) is an objective, reproducible measure of functional capacity. It was originally designed for use in patients with chronic obstructive pulmonary disorders and has been found to be a reproducible and valid outcome measure (Singh et al, 1992, 1994).

It has been used for patients attending Pulmonary Rehabilitation as a means of:

- 1. determining appropriate exercise intensity for individuals
- 2. identifying an appropriate home walking programme
- 3. measuring changes in functional capacity pre-and post-training.

The test is usually carried out by a Chartered Physiotherapist and, before testing, a thorough assessment of the patient is needed to ensure the relevance and safety of testing.

Criteria	✓
Blood pressure adequately controlled SBP < 180 mm Hg	
No angina at rest/unrelated to exertion	
Subject has taken all prescribed medication	
Subject free from sore throat, a cold or other temporary illness	
No orthopaedic problems that would be exacerbated by exercise	
Testing being done ideally at least 2 hours after subject has eaten	
meal	
Resting pulse regular and less than 100 bpm	
If subject diabetic, no hypoglycaemic episodes in past week	
No strenuous physical activity on day of testing	
Subject has suitable clothing/footwear	
Subject gives informed consent (verbal)	
Tester competent in basic life support	
Access to telephone in emergency	

Table 1 Pre-Test Checklist for Shuttle Walking Test

The test itself is a scaled down version of a Bleep Test (Leger and Lambert, 1982) which involves walking around a course identified by two cones (see fig1).

[figure not shown]

Figure 1 Plan of Shuttle Walk Test course

The walking speed is externally paced and increases each minute (see Table 2).

LEVEL	SPEED					
	mph	kmph				
1	1.12	1.8				
2	1.5	2.4				
3	1.88	3.0				
4	1.26	3.6				
5	2.64	4.3				
6	3.02	4.9				
7	3.4	5.5				
8	3.78	6.1				
9	4.16	6.7				
10	4.54	7.3				
11	4.92	7.9				
12	5.3	8.5				

Table 2 Shuttle Walking Test

It is important to know what limits a patient's exercise tolerance and so the test is 'symptom-limited'. In other words subjects are asked to keep going until they develop symptoms and are unable to continue with the test (e.g. leg fatigue, breathlessness).

Subject unable to keep up with set pace; the set pace is defined as arriving within 0.5 metres from the cone when bleep sounds

At subject's request e.g. shortness of breath, leg fatigue, pain

At operator's discretion if concerned re: subject's physical status e.g. oxygen saturation level, angina, dizziness

Table 3 Endpoints for Sub Maximal Shuttle Walking Test

The equipment needed and protocol for carrying out the test are shown in Tables 4 and 5.

Quiet, private area with non-slip surface				
Minimum floor space of 15m x 3m				
Shuttle Walking Test CD ¹				
CD player				
Stopwatch for pre-test calibration				
2 cones set 9 metres apart				
Pulse oximeter				
Borg breathlessness and RPE scales				

¹available from Department of Respiratory Medicine, University Hospitals of Leicester, [name].

Table 4 Equipment needed for Sub Maximal Shuttle Walking Test

- Go through Pre-Test Checklist (Table 1) with subject. If answer to any response is 'No' or 'Don't Know', then do not carry out test
- Set marker cones 9 metres apart
- Fit patient with pulse oximeter
- Explain Borg ratings of breathlessness and perceived exertion (RPE) and ensure subjects understand how to use these
- Play the instructions on the CD to the patient
- Clarify the endpoints of the test with subject (See Table 3)
- Walk round with the patient for the first or two minutes to help them establish the correct pace (starting pace is approximately 1 mph)
- Tell subject about an increase in walking speed just prior to the next triple bleep
- Discourage subjects from talking while they are doing the test
- Record total distance walked in metres, heart rate and oxygen saturation immediately once sitting
- Record reason for stopping test

Table 5 Protocol for Sub Maximal Shuttle Walking Test

Note: Most exercise tests are subject to a practice effect, i.e. a second test performed soon after the first, but before any exercise training is undertaken, generally yields an improved outcome measure. It is therefore always preferable to conduct a practice walk and to use the measurement from the second walk as the 'baseline' measurement. Without this, any improvement in post-training outcome is likely to be exaggerated.

Appendix 3.5: Modified Fried Criteria

- (a) Unintentional weight loss of > 10 pounds in last year
- (b) Grip strength weakness (< 30 kg in males/< 20 kg in females (in strongest hand)
- (c) Exhaustion as determined by 2 questions from CES-D questionnaire
- (d) Slowness: established cut off for 4 metre timed walk adjusted for sex and height
- (e) Low physical activity: Godin-Shephard Leisure Time Index in lowest quintile of normative data stratified by age and sex.

[figure not shown]
Appendix 3.6: Self-Efficacy for Exercise Survey

Self efficacy questionnaire

How confident are you right now that you could exercise three times per week for 20 minutes if:

1.	The weather was bothering you?	0	1	2	3	4	5	6	7	8	9	10
2.	You were bored by the program or activity?	0	1	2	3	4	5	6	7	8	9	10
3.	You felt pain when exercising?	0	1	2	3	4	5	6	7	8	9	10
4.	You had to exercise alone?	0	1	2	3	4	5	6	7	8	9	10
5.	You did not enjoy it?	0	1	2	3	4	5	6	7	8	9	10
6.	You were too busy with other activities?	0	1	2	3	4	5	6	7	8	9	10
7.	You felt tired?	0	1	2	3	4	5	6	7	8	9	10
8.	You felt stressed?	0	1	2	3	4	5	6	7	8	9	10
9.	You felt depressed?	0	1	2	3	4	5	6	7	8	9	10

Appendix 4: Knowledge Translation Strategy

Appendix 5: COVID-19 Assessment Procedure

Renal Rehab Assessment COVID-19 Operating Procedure

- Participants only on intervention for 1 month will be approached to re-start the entire study again at HSC and SOGH (completed Mar 16, 2020)
- Controls continue
- No active participants currently at SBGH

Study Recruitment:

On hold until future

Activity Logs

 Will be collected by [name] and [name] (study kinesiologists) by phone or email following the timeline of the protocol

Baseline Assessments:

On hold until future

Assessments 2-4

- Questionnaires (DSI, Self Efficacy, EQ-5D-5L, Godin-Shephard Physical Activity) will be either:
 - Conducted over the phone ([name] or [name] will phone participants)
 - Emailed to participants to be filled out and emailed back (emailed by [name] or [name])
 - Mailed to participants with a postage-paid envelope for return to CDIC (mailed by [name] or [name])
- Recovery time, hospitalization since last assessment, exhaustion, and weight loss questions should still be asked

Accelerometers

- Will not be sent out via mail to participants to avoid potential transmission of COVID-19
- o Accelerometer data will not be collected at this time

• Participant Reimbursement

- When assessments are completed the participant will be mailed a \$25
 VISA/Mastercard gift card and a signature page with a postage-paid envelope for return
 - This envelope should be addressed to be returned to CDIC
- o [name] (research coordinator) will be mailing the gift cards out from home
- Participant addresses will be emailed to her over the secure WRHA email in a password protected document and deleted once letter addressed

- Signature pages will be collected in CDIC and given to [name] to compile and determine if a participant needs to be contacted again
- Physical Tests (Shuttle Walk, Gait Speed, Hand Grip Strength)
 - Unable to be completed at this time
- Clinical Outcomes Data Collection (chart reviews)
 - Chart reviews for assessments conducted after March 16th will be completed once research staff are able to return to work on dialysis units

Site Specific Procedure

Sherbrook Dialysis Unit ([name] still required to report to work for clinical component of his position as per Manitoba Renal Program)

- Call participant a week before scheduled assessment to select a time that works for them
- 2. Call participant day of assessment at chosen time and go over questions and questionnaires
- 3. Tell participant to expect \$20 in an envelope given to them by a nurse and a signature page for them to sign
- 4. Call participant to confirm receiving \$20 and to remind them to return the signature page to their HD nurse who will drop this envelope off in [name]'s SCDU office mailbox
- 5. Confirm that signature sheet was returned signed and dated with [name] or [name]

Health Sciences Centre Dialysis Units (CDU, PHDU, GG7) and Seven Oaks Units

- Call participant a week before scheduled assessment to select a time that works for them
- 2. Call participant day of assessment at chosen time and go over questions and questionnaires
- 3. Tell participant to expect a \$25 gift card in the mail along with a signature page and a postage-paid envelope
- 4. Mail out gift card to participant with signature page and a return postage-paid envelope once assessment is complete

5.	Call participant to confirm receiving the gift card and to remind them to return the
	signed signature page via mail to CDIC

6.	Confirm	that signature	page was retur	ned signed and	dated with	[name] or [name]
----	---------	----------------	----------------	----------------	------------	-----------------

St. Boniface Dialysis Units

No active participants

^{*} Mail option will be given to participants who do not want to or are unable to complete the questionnaires via phone or email.

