5.5.1 Independent Data Safety Monitoring Board (DSMB)

The DSMB will be composed of 2 third party researchers and a statistician/analyst (Drs. [name] and [name] – University of Calgary, AB; [name], University of Manitoba). Safety data will be reviewed at least yearly at planned DSMB Data Review Meetings. Serious adverse events (see below) will be reported and reviewed immediately by the DSMB Chair. The DSMB will provide recommendations for continuation or early termination of the trial

based on assessment of safety. The DSMB may also make recommendations related to the selection, recruitment or retention of participants, their management and adherence to protocol-specific regimens, and the procedures for data management and quality control.

5.5.2 Ascertainment and Documentation of Adverse Events for DSMB:

- 1. At each study assessment visit, study participants will be asked by the independent outcome assessor at clinic if they have experienced any of the adverse (AE) or serious adverse events (SAE) on the list below.
- 2. In addition, the research coordinator will identify any AEs or SAEs through review of participants' hemodialysis charts at each assessment time point.
- 3. Study kinesiologist and research coordinator will also track events if noted during their interaction with patients.
- 4. Study staff will communicate with dialysis staff to inform them regarding the types of issues that constitute AEs and SAEs. Dialysis staff will be asked to report any such occurrences to study staff as soon as possible.

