5.5.3 List of Adverse Events to Be Collected for DSMB

Adverse Events:

- 1. Fistula blow
- 2. Muscle aches or pains
- 3. Symptomatic Intradialytic hypotension (BP < 90 mmHg or 20 mmHg drop from baseline associated with symptoms such as headache, cramping, dizziness, nausea)
- 4. Intradialytic cramping
- 5. Increasing fatigue
- 6. Symptomatic hypoglycemia (sugar < 4 associated with typical symptoms of hypoglycemia)
- 7. Fall
- 8. Foot ulcer

Serious Adverse Events:

- 1. Chest pain while exercising (either intradialytic or outside of dialysis)
- 2. Arrhythmia while exercising (either intradialytic or outside of dialysis)
- 3. Unstable hemodialysis necessitating transfer to emergency post hemodialysis
- 4. Tendon rupture
- 5. Fall with fracture
- 6. Admission to hospital for any cause
- 7. Acute coronary syndrome
- 8. Death from any cause

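### Appendix 5 does not carry the 5.5.3 adverse event list over to remote Assessments 2-4 and defers chart review, so prompt systematic capture of events without admission is not provided for

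*Combined protocol and SAP*

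**What the plan says.** Section 5.5.2 sets out four ways of finding adverse events.

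- **Route 1, direct questioning.** At each assessment visit, "study participants will be asked by the independent outcome assessor at clinic if they have experienced any of the adverse (AE"; the sentence goes on to serious events and points to the list in 5.5.3.
- **Route 2, chart review.** "the research coordinator will identify any AEs or SAEs through review of participants' hemodialysis charts at each assessment time point".
- **Route 3, contacts.** "Study kinesiologist and research coordinator will also track events if noted during their interaction with patients".
- **Route 4, dialysis staff.** They are told which events count, and "Dialysis staff will be asked to report any such occurrences to study staff as soon as possible".

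The list in 5.5.3 has 8 adverse events and 8 serious adverse events. The study schedule in Section 7.3 marks adverse event monitoring at visits 1 to 4.

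Appendix 5 replaces the clinic contact at Assessments 2-4. It begins with "Questionnaires (DSI, Self Efficacy, EQ-5D-5L, Godin-Shephard Physical Activity) will be either" and offers phone, email or mail. It then states: "Recovery time, hospitalization since last assessment, exhaustion, and weight loss questions should still be asked". It also says what stops for now: accelerometry and the physical tests. On charts it says: "Chart reviews for assessments conducted after March 16th will be completed once research staff are able to return to work on dialysis units". The 5.5.3 list appears neither among the items kept nor among those stopped.

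**The concern.** Routes 1 and 2 are the only two in 5.5.2 that work through every participant at every time point. Appendix 5 does not provide for the first at a remote visit and delays the second, both over the same period. Routes 3 and 4 continue, but they depend on an event being noticed or mentioned.

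Three things are at stake.

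- **Completeness.** Section 8.1 plans frequency tables of events by treatment group. An event that nobody asks about and no chart records will not reach them.
- **Timing.** Section 5.5.1 wants serious events reviewed by the DSMB Chair at once. An event first found in a deferred chart review arrives late. New arrhythmia and tendon rupture also count toward the safety criterion for suspending or stopping the study in Section 5.5.
- **Even-handedness.** Section 7.3.2 blinds the outcome assessors. The kinesiologist delivers the intervention and dialysis staff help set up and monitor the cycling (Section 7.4.2), so both may know the arm. If detection rests mainly on them, it could differ between arms.

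Exposure may also continue. Apart from participants about one month into the intervention, who are to be approached to start again, Appendix 5 does not say what those in the exercise arm do. Home resistance exercise needs no access to the unit.

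**Working it through.** The plan gives no figure to reproduce. The check sets the 5.5.3 list against what Appendix 5 keeps.

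**Routes.** Of four, one is not provided for remotely (direct questioning), one is deferred (chart review) and two are unchanged on paper (contacts and dialysis staff).

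**Events.** The list has 8 + 8 = 16 items. The grouping is mine, from the wording of the items:

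- Asked directly by a retained question: admission to hospital (1).
- Likely to surface through the admission question or unit records: acute coronary syndrome, death (2).
- Partly overlapping with the exhaustion question or a DSI item: muscle aches, increasing fatigue, chest pain while exercising (3).
- Treated here as arising in the unit, where staff can see them: fistula blow, symptomatic intradialytic hypotension, intradialytic cramping, unstable hemodialysis with transfer to emergency (4).
- No retained question unless an admission follows, and able to happen away from the unit: fall, foot ulcer, hypoglycemia (listed as "Symptomatic hypoglycemia (sugar < 4 associated with typical symptoms of hypoglycemia"), arrhythmia while exercising outside dialysis, tendon rupture, fall with fracture (6).

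Total: 1 + 2 + 3 + 4 + 6 = 16. The last group is 6 of 16, made up of 3 adverse events and 3 serious adverse events.

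**What the DSI can cover.** Its instructions in Appendix 3.1 ask about the past week. Assessments fall at baseline, 12, 26 and 52 weeks, so the intervals are 12, 26 - 12 = 14 and 52 - 26 = 26 weeks. One week is 1/12 = 8.3%, 1/14 = 7.1% or 1/26 = 3.8% of the interval. The DSI answers are also collected as an efficacy outcome, and nothing in Appendix 5 routes a positive item into adverse event recording.

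**How often routes 3 and 4 have contact.** Appendix 5 keeps activity logs on the protocol timeline, by phone or email. Section 7.1 sets that as weekly for 12 weeks, then every 2 weeks for 40 weeks. Participants also still attend dialysis. The 12 to 26 weeks is therefore the gap between formal assessments, not a gap in contact.

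**The case against.** The strongest reply is that the gap is inferred from silence. Appendix 5 is explicit about what stops, and adverse event questioning is not among those items. Nothing in it revokes 5.5.2, the schedule in 7.3, or Section 8.3, which lists questioning the participant as a means of detection and runs collection to the end of the study. The line of questions to keep can be read as a list of outcome items rather than a full visit inventory; death is also scheduled at visits 2 to 4 and is not mentioned there. The site steps tell callers to go over questions and questionnaires, without limiting which questions. Log contacts and dialysis staff reporting continue.

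Much of this stands, and it rules out three stronger readings that a reader might infer.

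- **That both systematic routes lapse.** The appendix commits to completing the chart reviews. Charted events remain recoverable, so the chart route loses timeliness rather than existence.
- **That remote participants are asked nothing about safety.** The hospitalization question elicits one listed serious event directly, and the exhaustion question and some DSI items overlap in part with others.
- **That a percentage of events is lost.** The documents give no yield for direct questioning, no count of participants assessed remotely, and no statement that an event at home goes uncharted. Recruitment is on hold and one centre has no active participants, so the number affected may be small.

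What the reply does not remove is the practical effect of an itemised operating list. It goes down to individual frailty questions yet leaves out the safety list, while the rule it would have to rely on is worded for the clinic.

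**Conclusion.** The point holds as a mismatch between Appendix 5 and Section 5.5.2. Staff who follow the appendix as written have no instruction to ask the 5.5.3 list at a remote assessment. Until charts are reviewed, events without admission would then be found only through log contacts and dialysis staff. On the grouping above this concerns 6 of the 16 listed events; a different view of which events arise in the unit, or how far the DSI overlaps, would move that count.

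The conclusion rests on reading the list of questions to keep as the working instruction. If staff went on asking the full list under 5.5.2, nothing was lost and only the text needs correcting. The documents show no effect on any comparison between arms and do not allow the number of missed events to be estimated. The possibility of unequal detection follows from who remains to notice events and is not demonstrated.

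**What to change.** Reconcile Appendix 5 with Section 5.5.2:

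1. Add the full 5.5.3 adverse event and serious adverse event list, asked for the whole interval since the last assessment, to the line of questions that are kept.
2. Put the same list in the phone script and, as a form, in the email and mail pack, with a follow-up call for any positive written answer.
3. For anyone already assessed remotely without the list, ask about that interval at the next contact.

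The cost is a few minutes per contact and one extra form. No additional visits are needed. Answers about an interval already past will depend on recall, so the third step recovers some of the information rather than all of it.
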